2.1. Study Rationale

Functional constipation is a common healthcare problem in children of all ages, with a worldwide prevalence ranging between 0.7% and 29.6% (Koppen 2018). Symptoms include infrequent, hard stools, and painful defecation and affected children may have abdominal pain and fecal incontinence, which is usually the result of fecal impaction leading to overflow incontinence. These symptoms can have a severe impact on a child's quality of life and may lead to school absenteeism and substantial costs related to healthcare utilization. Initial nonpharmacological interventions include education, behavioral modifications, and keeping a bowel diary. Despite these interventions, many children require pharmacological interventions. Treatment consists of disimpaction (ie, removal of the rectal fecal mass), followed by maintenance treatment and eventually a weaning phase. Multiple pharmacological agents are available for the treatment of FC in children. Despite chronic pharmacological treatment, approximately 40% of children with FC referred to a pediatric gastroenterologist remain symptomatic after 5 years and 20% of children still have symptoms after 10 years. In some cases, symptoms may persist into adolescence or adulthood despite medical treatment. Potential reasons for ineffectiveness of treatment include suboptimal dosage regimens, poor compliance with treatment, or the use of drugs with action mechanisms that do not address the underlying pathophysiological etiology.

There are no approved products for FC in children. Thus, effective treatments are needed to provide symptomatic relief in children and adolescents with FC, with the evidence for the safety and efficacy of these based on the results of adequate and well-controlled studies in children.

For the primary and key secondary endpoints in the Phase 2 dose-ranging LIN-MD-62 study in children, 6 to 17 years of age, none of the 3 linaclotide doses (A [low dose], B [medium dose], and C [high dose]) indicated clear improvement over placebo (p-value \geq 0.1502) based on the ITT population. However, a numerical trend towards efficacy at the higher doses was observed

for the primary endpoint of change from baseline in 4-week overall SBM frequency rate (SBMs/week). In addition, the safety profile was consistent with prior adult linaclotide studies in CIC.

As linaclotide was well tolerated across all doses tested in 6 to 17-year old participants treated in LIN-MD-62, LIN-MD-67 is being initiated in younger children with the primary objective of evaluating the dose response, safety, and efficacy of 4 weeks of linaclotide in pediatric participants, 2 to 5 years of age, with FC.

2.2. Background

2.2.1. Adult Linaclotide Program

Linaclotide has been developed by the sponsors, Allergan Sales, LLC and Ironwood Pharmaceuticals Inc., and is approved at 72 μg and 145 μg for the treatment of CIC and 290 μg for the treatment of IBS-C in adults. The adult linaclotide clinical development program that culminated in FDA and EMA approvals included the following studies conducted in North America.

- 4 large double-blind, placebo-controlled Phase 3 registration studies (2 IBS-C studies [LIN-MD-31 and MCP-103-302] and 2 CIC studies [LIN-MD-01 and MCP-103-303])
- 2 long-term adult safety studies (LIN-MD-02 and MCP-103-305), each with 78-week study intervention periods
- 3 randomized, double-blind, placebo-controlled, parallel-group studies (1 IBS-C study [Phase 3b study MCP-103-312] and 2 CIC studies [Phase 3b study LIN-MD-04 and Phase 3 study MCP-103-309]) have been completed.

Safety data from these adult studies showed that, except for diarrhea, the proportion of participants reporting a TEAE was similar between placebo and each linaclotide dose group, in the IBS-C and CIC studies, and the incidence of TEAEs was not dose-related.

With the exception of the gastrointestinal (GI) System Organ Class (SOC), (due to, as previously stated, the disproportionately high reporting of diarrhea in patients taking linaclotide), the occurrence of TEAEs in the CIC and IBS-C participants was balanced across study intervention groups in each SOC for the adult Phase 3 placebo-controlled studies. Diarrhea was the most frequently reported TEAE in linaclotide-treated CIC and IBS-C participants, consistent with its pharmacology; however, diarrhea was rarely associated with serious sequelae such as dehydration, fecal incontinence, or defecation urgency.

SAEs were infrequent and balanced across study intervention groups within each indication, and there were no SAEs of diarrhea reported. An analysis of the SAEs across the entire clinical development program revealed no pattern to suggest that linaclotide causes any specific serious condition.

Minor abnormalities in laboratory, vital sign, or ECG parameters were observed rarely; overall, there were no clinically meaningful differences between linaclotide and placebo study intervention groups for any of these parameters in the Phase 3 placebo-controlled studies in adults.

Additional registration studies were conducted outside of North America, which supported the approval of linaclotide for the treatment of IBS-C and CC in Japan and IBS-C in China. Results from these studies were consistent with those studies conducted in North America (linaclotide IB).

2.2.2. Pediatric Linaclotide Program

A total of 214 pediatric participants were treated with linaclotide in two Phase 2 dose-ranging studies in the FC and IBS-C pediatric populations (LIN-MD-62 and LIN-MD-63, respectively).

LIN-MD-62 was a Phase 2 double-blind, placebo-controlled, parallel group, safety and efficacy study of a range of linaclotide doses administered to participants, 6 to 17 years of age, who fulfilled modified Rome III criteria for FC (refer to Table 2–1 for dosing information). The objective of LIN-MD-62 was to evaluate the dose response, safety, and efficacy of 4 weeks of study intervention with 1 of 3 linaclotide doses (Dose A, B, and C) or 145 μ g (as an exploratory objective in the adolescent participants, 12 to17 years of age, using the approved adult dose) compared with placebo in pediatric participants who fulfill modified Rome III criteria for child/adolescent FC with the goal of selecting an optimal dose of linaclotide to evaluate in a confirmatory study.

A total of 173 participants were randomized to receive 1 of 3 proposed linaclotide doses (Dose A, B, and C) for pediatrics (n = 116 participants), the approved adult linaclotide dose (145 µg, n = 16 participants), or placebo (n = 41 participants) for 4 weeks of study intervention followed by a 1-week Postintervention Period (Table 2–1). For the primary and key secondary endpoints in the Phase 2 dose-ranging LIN-MD-62 study, none of the 3 linaclotide doses (A [low dose], B [medium dose], and C [high dose]) indicated clear improvement over placebo (p-value \geq 0.1502) based on analysis of the ITT population. However, a numerical trend toward efficacy at the higher doses was observed for the primary endpoint of change from baseline in 4-week overall SBM frequency rate (SBMs/week). Overall, linaclotide was well tolerated across all doses and both age groups. The safety profile was consistent with prior adult linaclotide studies for CIC. The most frequently reported TEAE was diarrhea, which occurred in 7.6% of linaclotide-treated participants versus 0% in the placebo group. The majority of the TEAEs of diarrhea reported were mild; none were severe. In the 12 to 17 years of age group, one participant experienced moderate diarrhea (related) leading to discontinuation in the linaclotide Dose C group.

There were no reported AESIs (ie, significant volume depletion and/or significant electrolyte abnormalities and/or ECG abnormalities that were considered by the investigator or sponsor to be related to diarrhea) or deaths. There were 2 SAEs (suicidal ideation and vomiting), each reported in 1 participant, in the 12 to 17 years of age group, neither were considered related to study intervention. Moreover, in the younger pediatric participants, 6 to 11 years of age, no SAEs or AEs leading to discontinuation were reported.

As with adults, linaclotide is minimally absorbed with low systemic availability in this pediatric population.

Dose Levels (µg) by Weight in Pediatric Participants Treated with Table 2–1 **Linaclotide in LIN-MD-62**

Age Group (Dose, μg)	Linaclotide Dose A N=36	Linaclotide Dose B N=41	Linaclotide Dose C N=39	Approved Adult Dose (exploratory) N=16
Participants 6-11 ye	ears			
18 to < 35 kg	9	18	36	-
≥ 35 kg	18	36	72	-
Participants 12 to 17	7 years			
	18	36	72	145

LIN-MD-63 was a Phase 2, multicenter, randomized, double-blind, placebo-controlled, parallel-group, safety and efficacy dose-ranging study of linaclotide in children ages 7 to 17 vears with IBS-C. The objectives of LIN-MD-63 were to evaluate the dose response, safety, and efficacy of 4 weeks of treatment with 1 of 3 linaclotide doses (Dose A, B, or C; refer to Table 2-2 for dosing information) or 290 µg (as an exploratory objective in the adolescent participants, 12 to 17 years of age, using the approved adult dose) compared with placebo in pediatric participants 7 to 17 years of age who fulfill the Rome III criteria for child/adolescent IBS and modified Rome III criteria for child/adolescent FC.

According to the original study design, approximately 260 participants with IBS-C were planned to be randomized in this study. However, due to slow participant enrollment, this study was terminated early based on FDA's feedback (Type C Meeting for pediatric IBS-C, June 2019). The actual sample size achieved was 101 randomized participants, which is approximately 39% of the original planned sample size. These 101 IBS-C participants were randomized to receive 1 of 3 proposed linaclotide doses (Dose A, B, and C) for pediatrics (n = 74 participants), the approved adult linaclotide dose (290 μ g, n = 8 participants), or placebo (n = 19 participants) for 4 weeks of study intervention. For the primary efficacy endpoint of change from baseline in 4-week overall SBM frequency rate, numerical improvement was observed with each increasing linaclotide dose compared with placebo based on analysis of the ITT population. For the key secondary efficacy endpoint of change from baseline in 4-week abdominal pain daytime symptoms, numerical improvement was observed with linaclotide 290 µg compared with placebo, while results were similar in the other linaclotide groups (Dose A, B, and C) compared with placebo.

Overall, linaclotide was safe and well tolerated across all doses and both age groups. The safety profile was consistent with prior adult linaclotide studies for IBS-C. The most commonly reported TEAE was diarrhea. The majority of the TEAEs of diarrhea reported were mild; none were severe. In participants 12 to 17 years of age, AEs leading to discontinuation were reported in 1 participant in the linaclotide Dose B group (diarrhea [related]) and 1 participant in the placebo group (abdominal pain, anaphylactic reaction [SAE], and hematemesis; all considered not related to study treatment). There were no AESIs (ie, significant volume depletion and/or significant electrolyte abnormalities and/or ECG abnormalities that are considered by the investigator or sponsor to be related to diarrhea) or deaths reported. There were 2 SAEs reported in participants 12-17 years of age (1 each in the placebo and linaclotide Dose A [36 µg] groups), neither of which were diarrhea, and neither were considered related to study intervention. Moreover, in pediatric participants 7 to 11 years of age, no SAEs or AEs leading to

As with adults, linaclotide is minimally absorbed with low systemic availability in this pediatric population.

Table 2-2 Dose Levels (μg) by Weight in Pediatric IBS-C Participants Treated with Linaclotide in LIN-MD-63

Age Group (years)	Weight (kg)	Linaclotide Dose A (μg) N = 29	Linaclotide Dose B (μg) N = 21	Linaclotide Dose C (μg) N = 24	Approved Adult Dose (μg) N = 8
7–11	18 to <35	18	36	72	-
	≥35	36	72	145	-
12–17	N/A	36	72	145	290

Additional information from studies conducted with linaclotide can be found in the linaclotide IB.

2.2.3. Other Nonclinical Information

2.2.3.1. Nonclinical Toxicology

discontinuation were reported.

In nonclinical studies, oral administration of linaclotide at 10 μ g/kg/day caused deaths in young neonatal mice (human age equivalent of approximately 0 – 28 days old). These deaths were due to rapid and severe dehydration produced by significant fluid shifts into the intestinal lumen resulting from GC-C agonism in neonatal mice. Supplemental subcutaneous fluid administration prevented death after linaclotide administration in neonatal mice. Tolerability to linaclotide increases with age in juvenile mice. In 2-week-old mice, linaclotide was well tolerated at a dose of 50 μ g/kg/day, but deaths occurred after a single oral dose of 100 μ g/kg. In 3-week-old mice, linaclotide was well tolerated at 100 μ g/kg/day, but deaths occurred after a single oral dose of

CONFIDENTIAL

linaclotide

 $600 \,\mu g/kg$. Significantly higher doses ($\geq 200 \,$ times the clinically relevant adult dose) were tolerated in 4-week-old juvenile mice, human age equivalent of approximately > 2 years old to 7 years old without supplemental fluid administration. Based on these nonclinical results, the Linzess PI (Jan 2017) has a contraindication in pediatric patients less than 6 years of age and a boxed warning regarding its use in pediatric patients.

2.2.3.2. GC-C mRNA Expression

Prior research suggested GC-C receptors may be present in younger children at a greater density than in adults (Guarino, 1987; Cohen, 1988). Greater GC-C receptor density in childhood could result in amplification of the pharmacological effects of GC-C activation, with important clinical implications for treating children with a GC-C agonist. Study MCP-103-311 was conducted to measure GC-C mRNA levels in duodenal and colonic mucosal tissue samples obtained from children, 0 to <18 years of age, who underwent endoscopy or colonoscopy. Four different age groups were evaluated ie, from birth to <24 months, 24 months to <6 years, 6 years to <12 years, and 12 years to <18 years.

The results showed that there was no trend toward an increase or decrease in GC-C mRNA expression based on age in either duodenal or colonic tissues. Along with results in LIN-MD-62 (Section 2.2.2), these results from study MCP-103-311 support a flat dosing approach for pediatric participants in the Phase 3 pediatric studies and not a body weight-based approach.

2.2.4. Post-marketing Experience

In post-marketing experience, severe diarrhea AEs associated with dizziness, syncope, hypotension and electrolyte abnormalities (hypokalemia and hyponatremia) requiring hospitalization or IV fluid administration have been reported in adult participants treated with linaclotide.

2.3. Benefit/Risk Assessment

Although not life threatening, FC is a common healthcare problem in children of all ages, with a worldwide prevalence ranging between 0.7% and 29.6% (Koppen 2018). Symptoms include infrequent, hard stools, and painful defecation and affected children may have abdominal pain and fecal incontinence, which is usually the result of fecal impaction leading to overflow incontinence. These symptoms can have a severe impact on a child's quality of life and may lead to school absenteeism and substantial costs related to healthcare utilization.

Linaclotide has a safety profile that has been well established in adults with IBS-C and CIC (linaclotide IB). Moreover, the safety profile in the first completed pediatric linaclotide study in FC, LIN-MD-62, was consistent with prior adult linaclotide studies in CIC. There were no new safety signals observed in the pediatric participants and linaclotide was well tolerated across all doses and age groups. Refer to the IB for a more detailed description of the chemistry, pharmacology, efficacy, and safety of linaclotide, based on studies conducted in animals, healthy volunteers, and in participants with IBS-C and CIC.

There are no pharmacologic therapies approved in the pediatric population specifically for the treatment of FC. Thus, there is a need for new agents with favorable safety and tolerability

profiles that are effective in providing relief for the variety of symptoms associated with FC in pediatrics.

Linaclotide provides an important treatment option for adult patients with FC. Linaclotide may offer a therapeutic option to treat the symptoms in the pediatric population with FC. The sponsors consider the benefit-risk balance is favorable and supports further clinical development of linaclotide as a treatment for FC in the pediatric population.

See Section 4, Study Design for details of study procedures, dose, and study design justification.

3. Objectives and Endpoints

The objective of LIN-MD-67 is to evaluate the dose response, safety, and efficacy of 4 weeks of study intervention with linaclotide compared with placebo in pediatric participants, 2 to 5 years of age, with FC.

Key efficacy endpoints include:

- Change from baseline in 4-week overall SBM frequency rate (SBMs/week) during the Study Intervention Period of each cohort
- Change from baseline in 4-week stool consistency reported by the caregiver during the Study Intervention Period of each cohort
- Change from baseline in 4-week straining reported by the caregiver during the Study Intervention Period of each cohort
- Proportion of days with fecal incontinence during the Study Intervention Period (for participants who have acquired toileting skills during the daytime and nighttime or acquired toileting skills during daytime only) within each cohort

The safety assessments will include monitoring of adverse events (AEs), clinical laboratory assessments (clinical chemistry, complete blood count [CBC], urinalysis), vital sign measurements (including postural vital signs), electrocardiograms (ECGs), physical examinations, height, and weight.

4. Study Design

4.1. Overall Design

Study LIN-MD-67 is a Phase 2 randomized, double-blind, placebo-controlled, sequential, ascending multidose study with a 4-week Study Intervention Period in participants, 2 to 5 years of age, who meet modified Rome III criteria for childhood FC.

Up to 30 participants, 2 to 5 years of age, will be sequentially enrolled into LIN-MD-67; eight participants each into Cohorts 1 to 3 and six participants in the final cohort. Participants will be randomly assigned to receive linaclotide or matching placebo as described below.

Number of Sites:

Up to 40 sites from the United States and Canada are expected to participate in the study.

Study Intervention Groups and Study Duration:

The study will consist of up to 4 cohorts, each of which will be 9 to 12 weeks in duration: 2 to 4-week Screening Period, a 2 to 3-week Preintervention Period, followed by a 4-week double-blind Study Intervention Period, and a 1-week Postintervention Period (Section 1.2).

Participants will not receive study intervention during the Screening/Preintervention Period and the Postintervention Period.

After at least 6 participants in Cohorts 1 to 3 complete at least 2 weeks of double-blind study intervention, an independent DSMB will review unblinded interim safety data. Based on this review, the DSMB will recommend whether the subsequent planned dose level should be tested. New participants will be recruited for each cohort.

[figure not shown]
Please refer to Figure 4-1 for assignment of participants to dose cohorts.

- Cohorts 1-3: 8 participants will be randomized at a ratio of 3:1 to receive linaclotide or matching placebo:
 - Cohort 1: linaclotide 18 μg or matching placebo once daily for 4-week Study Intervention Period.
 - Cohort 2: linaclotide 36 μg or matching placebo once daily for 4-week Study Intervention Period. The DSMB will have the option to recommend the lower dose of linaclotide μg instead of the 36 μg dose, based on review of unblinded interim safety data from Cohort 1.
 - O Cohort 3: linaclotide 72 μg or matching placebo once daily for 4-week Study Intervention Period. Participants will only be assigned to this cohort if the DSMB recommends proceeding to this 72 μg dose based on unblinded interim safety data from Cohort 2 with the linaclotide 36 μg dose.
- Final Cohort: 6 participants will be randomized at a ratio of 5:1 to receive linaclotide at the highest dose tested/determined to be safe or matching placebo for 4-week Study Intervention Period (ie, 18, 36, 72 μg depending on the recommendation of the DSMB).

Figure 4-1 Assignment of Participants to Dose Cohorts

Sponsor decision on how to proceed with the study is based on DSMB feedback following review of all available safety data prior to each subsequent cohort.

4.2. Scientific Rationale for Study Design

The purpose of this Phase 2 study is to investigate the potential therapeutic dose(s) of linaclotide in the target pediatric subset of participants, 2 to 5 years of age, with FC. Given the current contraindication under 6 years of age, as well as the lack of clinical data in this younger age group, a sequential, ascending multidose escalation design was selected.

4.3. Justification for Dose

[figure not shown]
Results from LIN-MD-62 suggested a lack of body weight normalized dose response in pediatric patients of age 6 to 17 years (Figure 4-2), which was also observed in adults (Studies MCP-103-201, LIN-MD-01, MCP-103-303, and MCP-103-309; Figure 10–1 in Appendix 11, Section 10.11). In addition, study MCP-103-311 showed that there was no trend toward an increase or decrease in GC-C mRNA expression based on age in either duodenal or colonic tissues. These data support a flat dosing approach for pediatric participants aged 2 to 5 years in the current dose range finding study.

The safety profile in the first completed pediatric linaclotide study in FC, LIN-MD-62, was consistent with prior adult linaclotide studies in CIC. There were no new safety signals observed

in the pediatric participants, and linaclotide was well tolerated across all doses and age groups. For participants in the 6 to 11 years age group in LIN-MD-62, the highest dose tested was 2 μ g/kg. The linaclotide dose selected for Cohort 1 in the current LIN-MD-67 study, 18 μ g, is consistent with the highest μ g /kg dose tested in LIN-MD-62 in the 6 to 11 years age group (not to exceed 1.8 μ g /kg) given minimum weight requirement for eligibility is 10kg. Dose escalation between cohorts will be implemented based on the review of all available safety/tolerability data by an independent DSMB.

Figure 4-2 Change from Baseline in 4-week Overall SBM Frequency Rate by Dose in μg/kg (ITT Population, LIN-MD-62)

Abbreviations: CFB = change from baseline; ITT = intent-to-treat; SBM = spontaneous bowel movement Source; Figure 14.2-1.3 of the LIN-MD-62 CSR

Assuming that the DSMB recommends proceeding to the next subsequent higher dose cohort, the following doses are planned to be tested in an ascending cohort design in the current study:

- Cohort 1: 18 μg (not to exceed 1.8 μg/kg, assuming minimum body weight of 10 kg*)
- Cohort 2: 36 μg (not to exceed 3.6 μg /kg, assuming minimum body weight of 10 kg*)
- Cohort 3: 72 μg (not to exceed 7.2 μg /kg, assuming minimum body weight of 10 kg*)

*10 kg =10% for 2-year old based on the CDC Stature for Age and Weight for Age percentiles in 2 to 20-year old boys (See Section 5.1, Inclusion Criteria 1.02)

Please refer to Section 4.1 and Figure 1-1 for assignment of participants to dose cohorts.

After at least 6 participants in each of the serial Cohorts 1 to 3 complete at least 2 weeks of double-blind study intervention, an independent DSMB will review unblinded interim safety

data. Based on this review, the DSMB will recommend whether the subsequent planned dose level should be tested. New participants will be recruited for each cohort.

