7.1.1. Removal of Individual Participants from Therapy or Assessment

Participants **must** be prematurely discontinued from the study for reasons of safety including those who experience:

- An SAE considered by the investigator or the sponsor to be possibly related or related to study intervention,
- An AESI (evidence of significant volume depletion and/or significant electrolyte and/or ECG abnormalities that are considered by the investigator or sponsor to be related to diarrhea) related to the study intervention (ie, intervention-related AESIs) see Section 8.3.1,

Participants **may** also be prematurely discontinued from the study for reasons of safety including those who experience:

• The presence of intentional overdose or intentional misuse per investigator discretion

- A vital sign, ECG, and/or laboratory abnormality judged to be clinically significant by the investigator and that in the opinion of the investigator or the sponsor is possibly related or related to the study intervention
- An intolerable AE (defined as an AE that subjectively would cause a participant to consider study withdrawal), see Section 6.1.1
- The occurrence of any other AE that in the opinion of the investigator or the sponsor is possibly related or related to the study intervention that represents a clinically significant safety risk to the participant

Additionally, discontinuation of study intervention for abnormal liver function should be considered by the investigator when a participant meets the criteria for Hy's law or the appearance of abnormal laboratory test results suggesting severe drug-induced liver injury (DILI) (refer to Appendix 9), or if the investigator believes that it is in the best interest of the participant.

All enrolled participants who prematurely discontinue from the study, regardless of cause, should be seen for the assessments to be completed at the EOT Visit. The EOT assessments are defined as completion of evaluations scheduled for all participants.

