7.1.2. Criteria for Consideration of Study Discontinuation

Dosing and enrollment will be immediately paused for all participants at all sites and a thorough review will be initiated after any one of the following conditions has been met in participants who have received study intervention at any time in the study:

- Any life-threatening SAE that is considered by the investigator or the sponsor to be possibly related or related to the study intervention.
- Any SAE resulting in death that is considered by the investigator or the sponsor to be possibly related or related to the study intervention.

In the event of a pause in enrollment and dosing, the Data Safety and Monitoring Board (DSMB) will be notified and their recommendation on an appropriate course of action will be sought. This may include resuming enrollment, continuing a hold on enrollment, resuming the study intervention, amending the protocol or stopping the study (Section 10.1.6.3). The decision to restart or to stop the study will be made by the sponsor, following a thorough review of all clinical, laboratory, DSMB recommendations and other available safety data.

In addition to the above, monitoring of participant safety data will be performed by the DSMB. Study conduct may be interrupted or terminated by the sponsor based on DSMB recommendation or if, following a thorough review of all clinical, laboratory, and other available safety data; safety data becomes available which appear to represent an undue risk to the study participants' health or well-being.

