7.2. Participant Discontinuation/Withdrawal from the Study

- A participant/parent/LAR may withdraw from the study at any time at their request or may
 be withdrawn at any time at the discretion of the investigator for safety, behavioral,
 compliance, or administrative reasons.
- If the participant/parent/LAR withdraws consent for disclosure of future information, the sponsor may retain and continue to use any data collected before such a withdrawal of consent.
- If a participant/parent/LAR withdraws from the study, they may request destruction of any samples taken and not tested, and the investigator must document this in the site study records.
- See the SoA for data to be collected at the time of study discontinuation and follow-up and for any further evaluations that need to be completed.

Participants in this study who prematurely discontinue study intervention will not be replaced.

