- Lack of efficacy or failure of expected pharmacological action per se will not be reported
 as an AE or SAE. Such instances will be captured in the efficacy assessments. However,
 the signs, symptoms, and/or clinical sequelae resulting from lack of efficacy will be
 reported as AE or SAE if they fulfil the definition of an AE or SAE.

Events NOT Meeting the AE Definition

- Any clinically significant abnormal laboratory findings or other abnormal safety assessments that are associated with the underlying disease, unless judged by the investigator to be more severe than expected for the participant's condition. Merely repeating an abnormal test, in the absence of any of the above conditions, does not constitute an AE. Any abnormal test result that is determined to be an error does not require recording as an AE.
- The disease/disorder being studied or expected progression, signs, or symptoms (clearly defined) of the disease/disorder being studied, unless more severe than expected for the participant's condition.
- The following disease-related events (DREs) are common in participants with FC and can be serious/life threatening:
 - Abdominal bloating
 - Straining
 - Sense of incomplete evacuation
 - Fecal incontinence

If the investigator considers these manifestations to have a reasonable possibility of relationship to the study intervention(s), then they should be reported as AEs or SAEs.

- Medical or surgical procedure (eg, endoscopy, appendectomy): the condition that leads to the procedure is the AE
- Situations in which an untoward medical occurrence did not occur (social and/or convenience admission to a hospital)
- Anticipated day-to-day fluctuations of pre-existing disease(s) or condition(s) present or detected at the start of the study that do not worsen

Definition of SAE

SAEs must meet both the AE criteria described above and the seriousness criteria listed below.

An SAE is defined as any untoward medical occurrence that, at any dose:

a. Results in death

b. Is life threatening

The term *life threatening* in the definition of *serious* refers to an event in which the participant was at risk of death at the time of the event. It does not refer to an event, that hypothetically might have caused death, if it were more severe.

c. Requires inpatient hospitalization or prolongation of existing hospitalization

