**13.1            DATA SAFETY MONITORING BOARD**

An independent DSMB will review unblinded interim safety data at defined intervals throughout the study. After at least 6 participants in Cohorts 1 to 3 complete at least 2 weeks of double-blind study intervention, the independent DSMB will review unblinded interim safety data. Based on this review, the DSMB will recommend whether the subsequent planned dose level should be tested. Further details of the DSMB (composition, policy, and procedures) are specified in a separate DSMB Charter.

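### No count-based pause within a cohort: three early related, non-life-threatening safety removals trigger no mandatory hold and put the planned DSMB review out of reach as worded

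*Protocol*

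**What the plan says.** Protocol 4.1 puts 8 children in each of Cohorts 1 to 3, randomized 3:1. The planned review that informs escalation comes, in protocol 4.3, "After at least 6 participants in each of the serial Cohorts 1 to 3 complete at least 2 weeks of double-blind study intervention". SAP 13.1 has the same condition: "After at least 6 participants in Cohorts 1 to 3 complete at least 2 weeks of double-blind study intervention".

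Protocol 7.1.1 lists events after which a child must leave the study. One is "An SAE considered by the investigator or the sponsor to be possibly related or related to study intervention"; another is an intervention-related AESI. Under the SAE definition in Appendix 3, an event is serious if it "Requires inpatient hospitalization or prolongation of existing hospitalization", so a hospitalization need not be life-threatening to count. Protocol 7.2 adds: "Participants in this study who prematurely discontinue study intervention will not be replaced".

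Protocol 7.1.2 contains the automatic hold: "Dosing and enrollment will be immediately paused for all participants at all sites and a thorough review will be initiated". It has two conditions. One is "Any life-threatening SAE that is considered by the investigator or the sponsor to be possibly related or related to the study intervention"; the other is a related SAE that results in death. When the hold applies, the DSMB is notified and asked for a recommendation. Otherwise 7.1.2 provides for DSMB monitoring of safety data and allows the sponsor to interrupt the study for undue risk. The Study Stop Rules entry in Appendix 6 repeats that provision. Section 10.1.6.3 provides for DSMB review at defined intervals or ad hoc, makes the Board advisory, and refers its procedures to a separate charter.

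**The concern.** The removal rule, the no-replacement rule and the review trigger work against each other. Early toxicity removes children from the pool of two-week completers, and the review waits for that pool to reach 6. The more early safety removals there are, the less likely the planned review is to be reached. The automatic pause does not fill the gap, because it depends on the type of event and not on the count: no number of related, non-life-threatening hospitalizations meets it.

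What is at stake is further enrollment and dosing at a level that has already produced several serious related events. Protocol 4.2 notes the contraindication under 6 years and the lack of clinical data in this age group. Protocol 2.2.4 records severe diarrhea in adults that needed hospitalization or IV fluids. Scheduled laboratory tests take place only at Screening and Week 4, so early harm would show mainly as clinical events, which a count rule would catch.

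**Working it through.** **Planned size.** 3 × 8 + 6 = 30, which matches protocol 9.2 and SAP 14.0. With 3:1 allocation, each of Cohorts 1 to 3 has 6 linaclotide and 2 placebo children.

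**Reaching the review.** Without replacement, the maximum number of two-week completers after k early removals is 8 − k.

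| Early removals k | Maximum completers | 6 reachable? |
|---|---|---|
| 0 | 8 | yes |
| 1 | 7 | yes |
| 2 | 6 | yes |
| 3 | 5 | no |

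Three is the exact point at which the condition fails. If all three were on linaclotide, 5 children remain in the cohort, 6 − 3 = 3 of them on linaclotide.

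**How likely.** The documents give no rate of related SAEs or AESIs at ages 2 to 5, so the risk p is an assumption. It stands for the chance that a linaclotide child has a mandatory safety removal. Children are treated as independent, with n = 6:

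P(X ≥ 3) = 1 − Σ(k = 0 to 2) C(6,k) p^k (1−p)^(6−k)

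P(X ≥ 2) = 1 − (1−p)^6 − 6p(1−p)^5

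| Assumed p | P(X ≥ 3): review unreachable | P(X ≥ 2): proposed pause fires |
|---|---|---|
| 1.7% | 0.01% | 0.4% |
| 5% | 0.2% | 3.3% |
| 10% | 1.6% | 11.4% |
| 20% | 9.9% | 34.5% |
| 30% | 25.6% | 58.0% |

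**The low anchor.** Protocol 2.2.2 reports 214 linaclotide-treated children in the two earlier pediatric studies, with no AESI and no SAE considered related. The exact 95% upper bound for 0/214 is 1 − 0.025^(1/214) = 0.0171, the first row of the table. That experience covers 4 weeks of treatment, whereas the shortfall needs removals before two weeks.

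**Limits of the anchor.** At the minimum weight of 10 kg, Cohort 3 receives 72/10 = 7.2 µg/kg. That is 7.2/2 = 3.6 times the top dose at ages 6 to 11 in LIN-MD-62 (protocol 4.3). It is 7.2/4.14 = 1.7 times the top dose at ages 7 to 11 in LIN-MD-63 (145/35 = 4.14 µg/kg, protocol Table 2-2). The children are also younger.

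**Pause rate if placebo children count too.** Relatedness is judged blind, so placebo events may be called possibly related. If all 8 children share a 5% risk, P(X ≥ 2) = 1 − 0.95^8 − 8(0.05)(0.95)^7 = 5.7%, against 3.3% for 6.

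**The case against.** The strongest reply is that judgment by an unblinded DSMB and an informed sponsor is an acceptable alternative to a count, and that both would have to stay passive after three related hospitalizations for harm to follow. Much of this stands. DSMB safety monitoring is planned, the Board can meet ad hoc, and the sponsor can interrupt the study (7.1.2, 10.1.6.3). SAEs are reported within 24 hours (Appendix 3). None of this sets a threshold or obliges anyone to pause.

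A reader might infer more than the documents support:

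- **That nothing written governs a stop.** Appendix 6 has a Study Stop Rules entry. It is judgment-based; what is missing is a count.
- **That the next dose could start without review.** Protocol 4.1 requires DSMB feedback on all available safety data before each subsequent cohort, and Cohort 3 needs a DSMB recommendation to proceed. Missing the 6-completer mark does not open that gate.
- **That the charter could not help because the Board is advisory.** Section 10.1.6.3 limits the Board's powers, not the charter's content. The charter may already hold a shortfall rule or a sponsor-executed hold.
- **That non-serious AESIs could pass unseen because only an eCRF entry is needed.** Protocol 7.1.1 has the sponsor contact the site after every premature discontinuation, Appendix 3 expects rapid communication of AESIs, and 8.3.4 requires updated AESI data within 24 hours.
- **That every related AESI forces removal.** Protocol 7.1.1 says must, but 8.2.3 and 8.2.4 say should for ECG and electrolyte AESIs and allow case discussion. The scenario therefore rests most securely on related SAEs.

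**Conclusion.** The point holds in a limited form. The protocol and SAP contain no count-based pause within a cohort, and three removals before Week 2 make the planned review unreachable as worded. The consequence is confined to continued enrollment and dosing in the affected cohort, for as long as no one uses the discretionary safeguards.

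The event is very unlikely if experience in older children carries over (about 0.01% per cohort at the upper bound). It becomes material only if the true risk is about 10% or more (1.6% at 10%, 9.9% at 20%). Those risks are assumptions, but guarding against a dose that proves toxic is what an escalation safeguard is for. Confidence is medium, mainly because the charter is not available. This is an inexpensive improvement worth considering, not a flaw that undermines the study.

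**What to change.** 1. **Review trigger.** In protocol 4.1 and 4.3 and SAP 4.0 and 13.1, hold the review at the earlier of two points: 6 children have completed two weeks, or every randomized child in a full or closed cohort has completed two weeks or discontinued. If the charter already says this, a cross-reference is enough. The DSMB would then judge whether fewer than 6 completers support a recommendation on the next dose.
2. **Count-based pause.** In protocol 7.1.2, add a pause of enrollment and dosing in the cohort, with DSMB notification, when a second participant in that cohort is discontinued under the mandatory safety criteria of 7.1.1. The sponsor and DSMB should confirm the number.

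The cost is one sentence in the review text and one condition in 7.1.2, with no added children or visits. The downside is an occasional unneeded pause: 3.3% per cohort at an assumed 5% risk in the 6 linaclotide children, or 5.7% if all 8 share that risk.
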